#### 16.2.2 Recording Adverse Events And Documentation In Velos

All AEs and SAEs regardless of causality must be entered in the Velos system. Unexpected and expected adverse events must be entered within 5 days and include:

- New unexpected adverse events
- Worsening baseline conditions
- Clinically significant laboratory findings
- Disease-related signs and symptoms that were not present at baseline
- Any event or finding that the Investigator feels is clinically significant

Documentation must be supported by an entry in the participant's electronic medical record file. A laboratory test abnormality considered clinically significant (requiring medical intervention) should be reported as an adverse event. Each event should be described in detail along with start and stop dates, severity, expectedness, relationship to investigational product, action taken and outcome.

#### 16.2.3 Serious Adverse Event Reporting

For serious adverse events, the clinical research site will follow local IRB policies and procedures.

All SAEs regardless of causality must be entered into Velos within 24 hours. Entering the event into Velos will send an automatic email to the KUCC Regulatory team and the KUMC DSMB. The PI's will notify Aclaris

Pharmaceutical, Inc, by email ([[contact]](mailto:[contact])) after the KUCC Regulatory team and DSMB have been notified.

Follow-up source documentation is required within 5 days.

Send all supporting documents with a cover sheet to:

KUMC DSMB  
Email: [[contact]](mailto:[contact])

#### 16.2.4 Summary Of Expedited Serious Adverse Event Reporting

	Relationship to Study Drug	IRB	Velos (KU DSMB and PI)	Funder
Unexpected SAE/AESI	Related	Per local IRB reporting policy	24 hrs	24 hrs
Unexpected SAE/AESI	Not-related	Per local IRB reporting policy	24 hrs	24 hrs
Expected SAE/AESI	Related	Per local IRB reporting policy	24 hrs	24 hrs
Expected SAE/AESI	Not-related	Per local IRB reporting policy	24 hrs	24 hrs

#### 16.2.5 SUBMITTING IND SAFETY REPORTS TO FDA

The University of Kansas Cancer Center Regulatory Affairs Department is delegated by the Sponsor-Investigator to report any IND safety report any suspected adverse reaction that is both serious and unexpected. Before submitting this report, the sponsor-investigator needs to ensure that the event meets all three of the definitions contained in the requirement:

- Suspected adverse reaction
- Serious
- Unexpected

If the adverse event does not meet all three of the definitions, it should not be submitted as an expedited IND safety report.

The following reports require expedited reporting.

- unexpected fatal or life-threatening adverse experiences associated with the use of the drug are to be reported by telephone or fax no later than 7 calendar days after initial receipt of the information [21 CFR 312.32©(2)]
- any adverse experience associated with the use of the drug that is both serious and unexpected is to be reported in writing no later than 15 calendar days after initial receipt of the information [21 CFR 312.32(c)(1)]

### 16.2.6 Reporting Of Pregnancy

While pregnancy itself is not considered to be an AE or SAE, any pregnancy complication or elective termination of a pregnancy for medical reasons will be reported as an AE or SAE. Abnormal pregnancy outcomes (e.g., spontaneous abortion, fetal death, stillbirth, congenital abnormalities, ectopic pregnancy) will be considered SAEs.

Monitoring for pregnancies in female patients will continue from the patient's inclusion in the study until the follow-up visit. Male patients will be required to inform the investigator if their partner becomes pregnant during the study. The investigator should inform the sponsor within 24 hours of learning of the pregnancy or partner pregnancy by completing and submitting a pregnancy report form to the sponsor (or designee).

If a patient becomes pregnant, study medication will be permanently discontinued, and she will be withdrawn from the study after completing the assessments planned for the end of study visit (see **Error! Reference source not found.**). Any pregnant patient and the fetus will be closely followed up throughout the duration of the pregnancy to determine the outcome (including spontaneous miscarriage, elective termination, normal birth, or congenital abnormality).

The investigator will ask the patient to provide informed consent to record information on the health of the baby. Generally, follow-up will be required for no longer than 6 to 8 weeks beyond the estimated delivery date.

While pregnancy itself is not considered to be an AE or SAE, any pregnancy complication or elective termination of a pregnancy for medical reasons will be reported as an AE or SAE. Abnormal pregnancy outcomes (e.g., spontaneous abortion, fetal death, stillbirth, congenital abnormalities, ectopic pregnancy) will be considered SAEs.

For any male study patient whose partner becomes pregnant, the investigator will attempt to collect pregnancy information on the male patient's partner while the male patient is in this study.

## 17 REGULATORY REQUIREMENTS AND DATA REPORTING

### 17.1 Institutional Review Board/Ethics Committee Approval

Before trial initiation this protocol and informed consent form will be submitted for review and approval by the IRB of record for the clinical site. Any form of proposed advertising and advertising text for patient recruitment must be reviewed and approved by the IRB. In accordance with FDA 21 CFR 56 of the Code of Federal Regulations the Investigator will forward the Sponsor/Investigator a copy of the IRB approval letter for the initial approval, amendments, informed consent and any informed consent updates.

The Investigator will be responsible for providing the Sponsor/Investigator a list of IRB members including profession and affiliation or a United States Department of Health and Human Services General Assurance number and expiration date. If neither of these is available, the IRB Chairperson must submit a statement indicating the members of the board responsible for the review meet the FDA and other appropriate

regulatory requirements. The labeling for all approved trial medications should be submitted to the IRB for information purposes.

Sub-sites will not be activated until the Sponsor/Investigator has received documentation of IRB approval.

## 17.2 Investigators Protocol Agreement

The Investigator must sign the Protocol Agreement before the study is activated. The original will be forwarded to the Sponsor/Investigator and the Investigator must retain a copy. The completed Investigator's Protocol Agreement signifies agreement to comply with all procedures outlined by this protocol by the Investigator. An Investigator's Protocol Agreement must be signed when a protocol amendment is issued.

## 17.3 Remaining Samples

Any samples remaining after the trial specified analyses is completed will be stored by the Sponsor/Investigator at the University of Kansas Biospecimen Repository Core Facility if the participant consented for use of their remaining samples for future research purposes. This includes the original specimen collected from the participant (blood, nasal cavity-nasopharynx specimens, bronchoalveolar lavage fluid and lung tissue specimens) as well as derivatives created from the original specimen (DNA, RNA, blocks or slides).

If a participant has not consented for their remaining samples to be used for future research purposes remaining samples and derivatives will be destroyed and documented.

## 17.4 Confidentiality

The Investigator and any other personnel involved in the trial shall not disclose or use for any purposes other than for the performance of this trial any data, records or other information disclosed to the Investigator or other trial personnel. Such information shall remain the confidential and proprietary property of the Sponsor/Investigator and shall be disclosed only to the Investigator or other designated trial personnel.

Participant confidentiality will be ensured by using assigned site-specific participant ID numbers throughout the trial.

## 17.5 Publication

The Sponsor/Investigator holds the primary responsibility for publication.

### **Data**

Aclaris and its co-development collaborator may use the data generated under the Research Agreement for all purposes, subject to Institutions right to unrestricted publishing.

**Publication**

KUMC Sponsor/Investigator shall publish the results of the approved study, subject to reasonable delay to allow for filing of patent applications on any inventions (as applicable). Sponsor/Investigator will provide Aclaris with the opportunity to review and comment on any publications, prior to submission.

**17.6 Compliance with Trial Registration and Results Posting Requirements**

Under the terms of the FDA Modernization Act (FDAMA) and the FDA Amendments Act (FDAA) the Sponsor/Investigator of the trial is solely responsible for determining if the trial and results meet the requirement for submission to the Clinical Trials Data Bank, <http://www.clinicaltrials.gov>. Information posted will allow participants to identify potentially appropriate trials for their disease conditions and pursue participation by calling a central contact number for further information on appropriate trial location and trial site contact information.

**17.7 Required Site Documentation**

Before the study is initiated at any site the following documentation must be provided to the Regulatory Department.

- A copy of the official IRB approval letter for protocol and informed consent.
- A copy of the IRB-approved consent form.
- CVs and medical licensure for the Principal Investigator and all Sub-Investigators who will be involved with conduct of the study.
- Appropriately completed and signed Form FDA 1572 with appropriate documentation.
- COP and CLIA Laboratory certification numbers and institution laboratory normal values.
- Executed clinical research contract.

**17.8 Data Management**

Web-based eCRFs will be used to collect participant data. All eCRFs and resulting data will be developed and maintained in a manner consistent with currently available regulations and guidance pertinent to the use of computerized systems in clinical trials. All users of the eCRF system will be trained prior to the use of the system.

A Risk-Based Monitoring (RBM) approach will be used focusing on critical variables and triggered events and ensuring the eCRF accurately reflects data recorded in source documents.

**17.9 Data Monitoring**

Data monitoring procedures will be carried out and will be performed on a regular basis to comply with Good Clinical Practice.

The study will be monitored at appropriate intervals, no less than those assigned per risk level designation, to assure compliance to GCP and to assess the data quality and study integrity.

Interim monitoring visits (IMV) will occur at regular intervals following enrollment/registration of the first study participant with the frequency and duration of each visit depending on recruitment status and participant enrollment/registration.

Review of the case report forms, cross-reference with source documents, review of trial related regulatory documents and logs will be monitored on an ongoing basis during monitoring sessions. The monitor will ensure that the trial is conducted according to protocol design and regulatory requirements.

The monitor will complete a follow-up letter and provide to the Sponsor/Investigator. The letter will include a summary of what the site monitor reviewed and the site monitor's statements concerning the significant findings/facts, deviations and deficiencies, conclusions, actions taken or to be taken and/or actions recommended to ensure compliance. The site will be expected to submit any Corrective and Preventative Action Plan (CAPA) in writing to the Sponsor/Investigator. A copy of the monitoring forms, follow up letter and CAPA will be kept in the site monitor's trial file and will be followed up at the next monitoring session.

The investigator and staff are expected to cooperate and provide all relevant study documentation in detail at each site visit on request for review. The study monitor will have direct access to source data for data verification. Data verification will be conducted by comparing the data entered into the CRFs with source data.

## 18 DSMB OVERSIGHT

The Data Safety and Monitoring Board (DSMB) of the University of Kansas Medical Center will monitor every participant receiving treatment on this protocol for safety, conduct and scientific progress of research protocols, and the validity and integrity of the data for clinical trials. This protocol will adhere to the policies of the currently approved Data and Safety Monitoring Plan which is in accordance with KUMC-IRB policy and guidelines. The committee is led by a senior practicing pulmonologist and consists of KUMC faculty and staff with expertise in pulmonology, critical care, research, and data management. The DSMB has the authority to require amendments, suspend, or terminate any research activities that fall within its jurisdiction, and can institute other appropriate actions as needed to protect participant safety.

The DSMB is an autonomous committee. However, its actions are communicated to other committees engaged in oversight of clinical research at KUMC. The PI is responsible for forwarding all DSMB letters, including those recommending continuation of the study, to the IRB and PRMC. The PI is notified of DSMB recommendations and is expected to alert all collaborating investigators about the DSMB action.

### 18.1 Serious Adverse Events

Serious adverse events that require expedited reporting will be reviewed by the DSMB Chair or designee who will determine if immediate action is required. If determined to be necessary by the DSMB, all participating sites will be notified of the event and any resulting action within one working day of this determination. In addition, all other active ATI-450 clinical trial sites (not associated with this protocol) will be informed about the INDSR.

NOTE: If expedited SAE report sent to FDA – then ALL sites with ATI-450 studies must be notified.

## 18.2 Review of Serious Adverse Event Rates

Once every two weeks, serious adverse event rates will be monitored by the DSMB Coordinator. If any study site has had 2 or more of the same treatment-related SAE reported within one month, or more than 6 of the same treatment-related SAE in 3 months, the DSMB will review summaries of SAEs, and discuss events in detail with the PI. The DSMB chair or designee determines whether further action is required. The Sponsor/Investigator, in collaboration with the DSMB Coordinator ensure that collaborating investigators and IRBs for all participating sites are notified of any resulting action.

## 18.3 Study Safety and Progress

An overall assessment of toxicities as described in the protocol is reviewed at DSMB meetings. This review enables DSMB committee members to assess whether significant risks are occurring that would warrant study suspension/closure or protocol amendment.

## 18.4 Quality Assurance Auditing

The study will be audited at appropriate intervals, no less than those assigned per risk level designation, to assure compliance to GCP and Good Documentation Practices (GCP).

The investigator and staff are expected to cooperate and provide all relevant study documentation in detail at each site visit on request for review. The study monitor will have direct access to source data for data verification. Data verification will be conducted by comparing the data entered into the CRFs with source data.

# 19 DATA HANDLING AND RECORD KEEPING

## 19.1 Data Collection and Management Responsibilities

Electronic case report forms (eCRFs) will be completed for each participant enrolled and registered on this study. All CRFs will be customized per this study, in order to emphasize completeness and accuracy. The investigatory and trained study staff will enter and edit the data via a secure network with secure identification and password requirements. A complete electronic audit trail will be maintained.

Source documents serve as the evidence of the existence of the participant and the data collected for this trial. Source documents will be the responsibility of the Investigator and will be filed at the site and available as needed by the Sponsor/Investigator or assigned Clinical Site Manager.

Data captured in the eCRF is to be transcribed from source documents and must be consistent with any discrepancies explained and document. The medical chart and any other clinical worksheets, procedural reports, etc. will be the source documentation of data captured into the study database.

## 19.2 Protocol Deviations

It is understood that deviations from the protocol should be avoided, except when necessary to eliminate an immediate hazard to a research participant. All deviations will be entered into the CRIS system must be reported to the DSMB. All deviations will be reported to the IRB per local reporting policy.

## 19.3 Study Closure

Upon study closure, the Sponsor/Investigator and/or Institution will be required to certify that all safety reporting obligations were met.

## 19.4 Study Records Retention

The investigator must prepare and maintain adequate and accurate case histories designed to record all observations and other data pertinent to the study for each research participant. This information enables the study to be fully documented and the study data to be subsequently verified. Original source documents supporting entries in the case report forms include but are not limited to hospital records and clinic charts, laboratory and pharmacy records, ECG, signed ICFs, participant diaries and pathology reports. All study-related documents must be retained for the maximum period required by applicable federal regulations and guidelines or institutional policies.

## 20 APPENDICES

### Appendix A: Reportable Events

#### Adverse Event (AE) Definition

Adverse event (AE) is defined as any new untoward medical occurrence or worsening of a preexisting medical condition in a clinical investigation participant administered study drug and that does not necessarily have a causal relationship to this treatment. An AE can therefore be any unfavorable and unintended sign (such as an abnormal laboratory finding), symptom or disease temporally associated with the use of investigation product, whether or not considered related to the investigational product.

#### Serious Adverse Event (SAE) Definition

A Serious Adverse Event (SAE) is any untoward medical occurrence that at any dose:

- Results in death.
- Is life-threatening (defined as an event in which the participant was at risk of death at the time of the event; it does not refer to an event which hypothetically might have caused death if it were more severe).
- Requires inpatient hospitalization or causes prolongation of existing hospitalization.
- Results in persistent or significant disability/incapacity.
- Is a congenital anomaly/birth defect
- Is an important medical event defined as a medical event or multiple medical events that may not be immediately life-threatening or result in death or hospitalization but, based upon appropriate medical and scientific judgement may jeopardize the participant or may require intervention (e.g., medical, surgical) to prevent one of the other serious outcomes listed above.
- Suspected transmission of an infectious agent (e.g., pathogenic or nonpathogenic) via the study drug.

Although pregnancy and potential drug-induced liver injury are not always serious by regulatory definition, for the purposes of this protocol, these events are considered to be an SAE and follow the SAE reporting timeline.

Any component of the study endpoints that is considered related to study therapy should be reported as an SAE (e.g., death is an endpoint, if death occurred due to anaphylaxis, anaphylaxis is reported an SAE.)

NOTE: The following hospitalizations are not considered SAE's:

- An Emergency room or other hospital department visit <24 hours that does not result in admission. Unless considered an important medical or life-threatening event)
- Elective surgery planned prior to signing consent.
- Admissions as per protocol for a planned medical/surgical procedure.
- Routine health assessment requiring admission for baseline/trending of health status. (e.g., routine colonoscopy)

- Medical /surgical admission other than to remedy ill health and planned prior to entry into the study. Appropriate documentation is required in these cases.
- Admission encountered for another life circumstance that carries no bearing on health status and requires no medical/surgical intervention. (e.g., lack of housing, economic inadequacy, caregiver respite, family circumstances, administrative reason)

### Unanticipated Problem

An Unanticipated Problem is any incident, experience or outcome involving risk to participants or others in any human participant research that meets all of the following criteria:

- Unexpected (in terms of nature, severity or frequency) given the research procedures described in the IRB-approved protocol and informed consent document and the characteristics of the population being studied.
- Related or possibly related to participation in such research (i.e., there is a reasonable possibility the incident, experience or outcome may have been caused by the procedures involved in such research).
- Suggests that the research placed participants or others at a greater risk of harm (including physical, psychological, economic or social harm) that was previously known or recognized.

### Suspected Adverse Reaction

A Suspected Adverse Reaction (SAR) is any AE for which there is a reasonable possibility that it was caused by the drug.

Reasonable possibility means there is evidence to suggest a causal relationship between the drug and the AE. Examples of reasonable possibility are:

- A single occurrence of an event that is uncommon and known to be strongly associated with drug exposure.
- One or more occurrences of an event that is not commonly associated with drug exposure but is otherwise uncommon in the population exposed to the drug.
- An aggregate analysis of specific events observed in a clinical trial that indicates that those events occur more frequently in the drug treatment group than in a concurrent or historical control group.

### Expectedness and Attribution

Both AE's and SAE's are evaluated with regard to expectedness and attribution.

#### Expectedness

Expected events are those that have previously been identified as resulting from administration of the agent. For the purposes of this study an event is considered expected when it appears in the Investigator's Brochure, the package insert or is included in the informed consent document as a potential risk.

An event is unexpected when it varies in nature, intensity or frequency from information provided in the

Investigator's Brochure, the package inserts or when it is not included in the informed consent document as a potential risk.

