### 1.3 Risk/Benefit Assessment

#### 1.3.1 KNOWN POTENTIAL RISKS

Immediate Risks	Acute neutropenia Upper respiratory infection Headache, dizziness
Long-range Risks	Unknown
Other Risks	Possible bacterial and fungal infection

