##### **Expectedness**

An adverse event “unexpected” if it is not listed in the investigator brochure or is not listed at the specificity or severity that has been observed; or, if an investigator brochure is not required or available, is not consistent with the risk information described in the general investigational plan or elsewhere in the current application. “Unexpected,” as used in this definition, also refers to adverse events that are mentioned in the investigator brochure as occurring with a class of drugs or as anticipated from the pharmacological properties of the drug but are not specifically mentioned as occurring with the Particular drug under investigation.

Events not listed in the investigator brochure are considered “unexpected” and those listed are considered “expected.”

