**Sponsor/Investigator Reporting to FDA**

The University of Kansas Medical Center's Sponsor/Investigator as holder of the IND will be responsible for all communication with the FDA. The Sponsor/Investigator will report any adverse event that is serious, unexpected and reasonably related (possible, probable, definite) to the study treatment.

The Sponsor/Investigator must report the following Suspected Adverse Events as outlined below:

Table 11-1

Event	Report To	Time Frame
Unexpected fatal or life-threatening SAR	FDA	As soon as possible but no later than 7 calendar days after the Sponsor/Investigator's initial receipt of the information.
Any event that is both serious and unexpected SAR	FDA and participating investigators	As soon as possible but no later than 15 calendar days after the Sponsor/Investigator's determine the information qualifies for reporting
Any findings from epidemiological studies, pooled analysis of multiple studies or clinical studies regardless if conducted under an IND or if the Sponsor/Investigator it suggests significant risk to humans exposed to the drug	FDA and participating investigators	As soon as possible but no later than 15 calendar days after the Sponsor/Investigator's determine the information qualifies for reporting
Any findings from animal or in vitro testing, regardless if conducted by the Sponsor/Investigator that suggests a significant risk in humans exposed to the drug	FDA and participating investigators	As soon as possible but no later than 15 calendar days after the Sponsor/Investigator's determine the information qualifies for reporting
Any clinically important increase in the rate of a Serious SAR over that listed in the protocol or Instigator Brochure.	FDA and participating investigators	As soon as possible but no later than 15 calendar days after the Sponsor/Investigator's determine the information qualifies for reporting

Expected SAE's and AE's should be included in the IND Annual Reports.

Follow-up information to a safety report should be submitted as soon as the relevant information is available. However, if the results of the Sponsor/Investigator determines an adverse drug experience not initially determined to be reportable are so reportable the Sponsor/Investigator must report such experience as soon as possible but no later than 15 calendar days after the determination is made.

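### Expectedness is defined differently in section 16.1.1 and Appendix A, so the same related serious event can need a 7- or 15-day FDA report or only an annual-report entry

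*Protocol*

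**What the plan says.** Two sections of the protocol define expectedness. The SAP text does not address it.

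- **Section 16.1.1, Expectedness.** An event is unexpected if "it is not listed in the investigator brochure or is not listed at the specificity or severity that has been observed". Other risk information counts only where no brochure is required or available. The term "also refers to adverse events that are mentioned in the investigator brochure as occurring with a class of drugs", or as foreseeable from the drug's pharmacology, where the brochure does not say that they have occurred with this drug. A closing sentence then reduces all this to a plain split: in the brochure, expected; not in it, unexpected.
- **Appendix A, Expectedness.** The opening sentence describes expected events as ones already found to result from giving the agent. The second sentence sets the working rule for this study. A listing in the brochure is enough to make an event expected, and so is either of two alternatives, namely that it is in "the package insert or is included in the informed consent document as a potential risk". A further paragraph makes an event unexpected if it departs in nature, intensity or frequency from the brochure or package insert, or "when it is not included in the informed consent document as a potential risk".

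The classification decides the FDA route. Section 16.2.5 requires an expedited report for a suspected adverse reaction that is serious and unexpected, and adds: "If the adverse event does not meet all three of the definitions, it should not be submitted as an expedited IND safety report". The limits are 7 calendar days for unexpected fatal or life-threatening events and 15 for other serious unexpected ones. Appendix A, Sponsor/Investigator Reporting to FDA, has its own table with the same limits and says that expected events "should be included in the IND Annual Reports".

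**The concern.** Both definitions are in force. Section 12 sends readers to Appendix A for adverse event information, and Appendix A holds a complete set of rules: its own definition and its own FDA table. Section 16 holds another set. The supplied text does not say which prevails. Two people who follow the protocol correctly can therefore classify the same event differently, depending on the section they open.

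The FDA report and the notices that depend on it are at stake. Sections 12.4 and Appendix A, Guidelines for Processing IND Safety Reports, pass these reports on to participating institutions. Section 18.1 ties notice to all other ATI-450 sites to an expedited report having gone to FDA.

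New bacterial or fungal infection shows how this might arise. Section 16.2.1 makes it the adverse event of special interest, and section 1.3.1 lists "Possible bacterial and fungal infection" among the risks. The common Phase 1 events in section 1.1.4.4 include upper respiratory tract infection but name no bacterial or fungal infection. A consent form could plausibly name such a risk before it has been seen with the drug.

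**Working it through.** No figure in the plan bears on this, so there is none to reproduce. The check applies each rule to the ways in which a risk can be listed, then follows a related serious event through the reporting rules.

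| Where the risk is listed | 16.1.1, main text | 16.1.1, closing sentence | Appendix A, second sentence | Appendix A, further paragraph |
|---|---|---|---|---|
| (a) Consent form only | Unexpected | Unexpected | Expected | Arguable: an unlisted event may be said to differ in nature from the brochure |
| (b) Brochure, at the observed specificity and severity, but not the consent form | Expected | Expected | Expected | Unexpected |
| (c) Brochure, only for the drug class or from pharmacology | Unexpected | Expected | Expected | Unexpected if also absent from the consent form; otherwise arguable |
| (d) Nowhere | Unexpected | Unexpected | Not expected | Unexpected |

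From the table:

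1. In (a), section 16.1.1 and the second sentence of Appendix A give opposite answers.
2. In (b), Appendix A contradicts itself. The brochure listing makes the event expected, and its absence from the consent form makes it unexpected.
3. In (c), the main text of 16.1.1 disagrees with Appendix A's second sentence. It also disagrees with its own closing sentence, which drops the class and pharmacology rule. That sentence drops the specificity and severity test as well.
4. Only in (d) do all the texts agree.

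Consequence for a related serious event in (a) or (c):

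- **FDA, under the main text of 16.1.1:** unexpected, so a report is due in 7 or 15 calendar days under section 16.2.5.
- **FDA, under the second sentence of Appendix A:** expected, so no expedited report, and the event goes into the annual report.
- **DSMB, regulatory department and funder, under either definition:** 24 hours. Sections 12.3 and 16.2.3 cover all serious events, and the table in 16.2.4 gives the same times for expected and unexpected events.

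On timing, the Protocol Summary gives a study duration of 9 months, and an annual cycle is 12. An event left to the annual report could therefore reach FDA after dosing has ended, depending on where the reporting date falls.

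**The case against.** **Appendix A can be read the other way.** Its opening sentence ties *expected* to what has already been seen with the agent, and its further paragraph makes departures from the brochure unexpected. On that reading a risk named only in the consent form, and never seen with ATI-450, is unexpected, as in 16.1.1. This stands to the extent that Appendix A is ambiguous in case (a). It does not remove the problem. The second sentence is the one that states the rule for this study, and it still says expected, so one section supports both answers.

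**A reader might infer that a related serious infection could escape expedited reporting altogether.** The documents do not support that. Section 12.3 requires a 24-hour report with a MedWatch form to the regulatory department, whatever the expectedness. That department is the one delegated in 16.2.5 to submit IND safety reports. Section 16.2.3 adds automatic notice to the DSMB, and 16.2.4 adds the funder. Section 16.2.1 requires a special-interest report for any new bacterial or fungal infection, whatever its severity.

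Other safeguards also make no use of expectedness. Section 9.1.3 sends such infections for evaluation by the 24-hour DSMB route, section 18.2 reviews serious event rates every two weeks, and section 15.7 sets a trigger for related grade 3 or higher events. Appendix A separately requires a 15-day report for a clinically important rise in the rate of a serious suspected reaction. This objection stands: early knowledge inside the trial is protected. None of the 24-hour routes is itself the FDA report, though, and notice to other ATI-450 sites hangs on that report.

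**The infection example depends on documents that are not supplied.** It needs the consent form to name infection, and the brochure either to omit it or to mention it only for the class or from pharmacology. If both documents list it for ATI-450 at the observed specificity and severity, both sections call it expected and the example falls away. This also stands, but the conflict in the text does not depend on the example.

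**Conclusion.** The point holds in limited form. The two definitions conflict, Appendix A contradicts itself on an event in the brochure but not in the consent form, and 16.1.1 is undercut by its own closing sentence. For a serious, related event in case (a) or (c), the difference is a report to FDA within 7 or 15 calendar days against an entry in the annual report. The notices to participating sites and to other ATI-450 sites that follow from an expedited report would be lost with it. Participating sites might still hear through DSMB action under sections 18.1 and 18.2, but that depends on the DSMB's judgement.

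The number of events affected cannot be estimated, because the brochure and consent form are not supplied. For the same reason bacterial or fungal infection is a possible example and not a demonstrated one. The analysis rests on a brochure being available, as the protocol's own references to it imply. Endpoints and statistical analyses are not affected. The conflict should be corrected because it concerns external safety reporting and costs little to remove.

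**What to change.** Keep one definition, in section 16.1.1:

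- The investigator brochure is the reference, at the observed specificity and severity.
- Events mentioned only for the drug class or from pharmacology remain unexpected.
- The existing fallback applies where no brochure is required or available.
- The closing sentence is deleted, or qualified so that a brochure listing counts only if it passes these tests. Copying 16.1.1 unchanged would carry its inconsistency along.

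Replace the Expectedness text in Appendix A with a cross-reference to 16.1.1. This removes the package insert and the consent form as grounds for calling an event expected.

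The change is to protocol wording only. Its downside is possibly a few more expedited reports.
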